2.3 Risks/Benefits

The proposed home visits and biosample and data collection itself pose minimal risk to participants. Anthropometric measurements are all non-invasive. There would be a blood draw (thus potential for brief mild pain) associated with any home visit (1 to 2 over the course of the study for any given participant). The study team will ensure that the amount drawn at any visit is safe from a blood volume standpoint. It is possible, but unlikely, that some survey questions may cause participants to feel uncomfortable. All instruments proposed have been previously used in other research.

For participants selected to participate in the randomized intervention trial, it is possible that receipt of clinical lab results may cause some participants to feel uncomfortable or anxious. Similarly, receipt of a SCP with an individual's predicted cardiovascular risk may cause anxiety or discomfort. We will be monitoring self-reported anxiety and depression as part of our study. Nevertheless, we feel that providing such information, even when unexpected, may be important and have important future health consequences, as the research data to be provided to participants are all results with clinical interpretation and significance. For participants on the intervention arm, they will get a telephone or web video session by which any results are given and explained to them by a survivorship trained clinician, approximating a normal clinical exchange. Participants on the control arm will only get a letter summarizing clinically relevant results, and will be encouraged to discuss any abnormal results with their primary healthcare provider. The study has in place, a process by which critical test results will be reported to the study team in real time, in which case, the PI or his designee, can notify the participant more quickly to seek medical follow-up. This process is similar to and adapted from that used by the CDC-sponsored NHANES for their in-person mobile assessments. For participants (either intervention or delayed control) with clinically actionable results but who have no current healthcare provider, the study team has access to resources to aid participants in finding providers in their area who have expertise in treating survivors of childhood cancer. This will be clearly explained on their results letter.

Control participants will get access to the SCP with personalized recommendations and a self-management counseling session with formal written summary "action plan" following the 2nd home visit if they chose to. Finally, all healthcare providers designated by the study participant will also receive a copy of the same clinically relevant study test results. Providers of intervention study participants also will receive a copy of the SCP with personalized recommendations following both home visits. SCPs are IOM-recommended documents now felt to be integral to cancer care, but whose efficacy in modifying

clinical endpoints has not been rigorously studied. Prior CCSS and other research also have shown that most cancer survivors have not previously received a SCP.

Among survivors found to be underdiagnosed or undertreated (Aim 1), in a randomized controlled design, compare changes in blood pressure, lipid, and blood glucose values from baseline to 1-year between those receiving the intervention (providing clinical results and survivorship care plans [SCPs] to participants and their healthcare providers, supplemented by clinician-led remote counseling sessions with participants to review SCP contents and teach CV risk factor self-management strategies) vs. control (providing clinical results without SCP to participants and their healthcare providers; with delayed access to the intervention).

- *Hypothesis: At the 1-year follow-up home visit, survivors randomized to the intervention arm will have a lower probability of having an undertreated CV risk factor compared with survivors in the control arm.*

3.1.3 Primary Aim 3

Determine barriers among (Aim 2) survivors (at baseline and 1-year: knowledge of

past cancer treatment, self-efficacy, health-related attitudes, medication adherence) and their primary healthcare providers (at 1-year only: knowledge and self-efficacy towards childhood cancer survivorship care) that contribute to undertreatment of hypertension, dyslipidemia, and diabetes.

- *Hypothesis 1: At baseline, underdiagnosis and undertreatment will be associated with lower knowledge, self-efficacy, and medication adherence, as well as a “self-controlling” health attitude among survivors.*
- *Hypothesis 2: At 1-year follow-up, intervention-arm participants will report improved knowledge, self-efficacy, and medication adherence vs. controls; healthcare providers who received the SCP will report improved knowledge and self-efficacy towards CV risk and survivorship care vs. providers of controls.*

3.2 Study Population

The study would seek to enroll ~800 current participants of the Childhood Cancer Survivor Study (CCSS) cohort, an existing NIH-funded resource study with >24,000 cohort members that has been actively funded for >20 years. The study would secondarily also survey participants' designated primary healthcare provider regarding knowledge and self-efficacy related to care of childhood cancer survivors.

3.3 Study Design

The study's first primary aim will be answered by recruiting a cross-sectional sample of predicted high CV risk patients. Those who meet eligibility criteria will then be randomized to a controlled intervention with delayed intervention controls to answer the study's second and third primary aims.

3.3.1 Primary Aim 1 Endpoint: Prevalence of underdiagnosis and undertreatment of the following target CV conditions. *Underdiagnosis* defined for each as:

- Hypertension: Joint National Committee (JNC7/8)^{47,48} considers systolic 120-139 and diastolic pressures 80-89 mmHg to be suggestive of pre-hypertension; *lifestyle intervention* is recommended.^{47,49} Hypertension is suspected if systolic ≥ 140 or diastolic ≥ 90 mmHg, and in addition to lifestyle modification, *pharmacologic treatment* is recommended for adults <60 years (treatment threshold ≥ 150 systolic if ≥ 60 years).⁴⁸ We will ascertain the prevalence of pre-hypertension and hypertension; both may be eligible for Aim 2. *However, with the introduction of the 2017 ACC/AHA hypertension guidelines, the classification system has shifted such that systolic ≥ 130 or diastolic ≥ 80 mmHg are now considered Stage 1+ hypertension (with treatment threshold reduced accordingly).*⁵⁰ As such, *with our 12/2017 protocol modification, we will adopt these slightly more stringent thresholds for eligibility and drop the prior “pre-hypertension” category.*
- Dyslipidemia: American Heart Association and American Academy of Pediatrics recommend intervening (*lifestyle modification first; if unsuccessful, consider pharmacologic therapy*) among childhood cancer survivors for LDL ≥ 160 mg/dL or fasting triglyceride ≥ 150 mg/dL.⁵¹ As fasting blood draws are not as commonly done in most primary care settings now for initial screening, for non-fasting (<10 hours) samples, a triglyceride ≥ 200 mg/dL is considered high. This study will use these cut-points to define dyslipidemia. These thresholds were largely in-line with

those defined by a recent NIH-sponsored expert panel,⁵² and largely similar to prior NCEP Adult Treatment Panel recommendations.⁵³

- **Diabetes:** American Diabetes Association classifies fasting blood glucose 100-125 mg/dL or HbA1c 5.7-6.4% as suggestive of impaired glucose tolerance (pre-diabetes). Similar to dyslipidemia, as fasting blood draws are not as commonly done in most primary care settings now for initial screening, for non-fasting (<8 hours) samples, blood glucose 140-199 mg/dL will be classified as suggestive of pre-diabetes if HbA1c was <5.7%. *Lifestyle intervention* is recommended (metformin prevention considered for select high risk populations).⁵⁴ Diabetes requires fasting blood glucose ≥ 126 mg/dL or HbA1c $\geq 6.5\%$. If not-fasting, random blood glucose ≥ 200 mg/dL would be concerning for diabetes if HbA1c was $<6.5\%$. In addition to lifestyle modifications, *metformin* is typically started with additional agents as indicated. We will ascertain the prevalence of pre-diabetes and diabetes; both may be eligible for Aim 2.

Undertreatment defined for each as:

- While any participant who was previously undiagnosed is also technically undertreated, we will reserve this definition to those who previously or currently reported to CCSS as being diagnosed with hypertension, dyslipidemia, or diabetes (either managed by lifestyle modifications or medication therapy), if their home-sampled value falls outside the recommended therapeutic range: blood pressure $\geq 130/80$ mmHg, LDL ≥ 160 mg/dL, triglyceride ≥ 150 mg/dL (if fasting <10 hours: ≥ 200 mg/dL), or HbA1c $\geq 7.0\%$ (different than the HbA1c diabetes diagnosis threshold⁶⁵).

3.3.2 **Primary Aim 2 Endpoint:** Probability of intervention subjects having an undertreated CV condition compared with the control group at 1-year follow-up.

3.3.3 **Primary Aim 3 Endpoint:** Barriers among survivors and their primary healthcare providers that contribute to undertreatment of hypertension, dyslipidemia, and diabetes.

3.4 Estimated Accrual

The proposal would seek to enroll up to 800 participants to answer Primary Aim 1. If 60% of those participants are found to have an abnormal CV condition, up to 480 would then be eligible to participate in the randomized controlled trial as part of Primary Aims 2 and 3 (n=240 in each study arm).

3.5 Sponsor/Funding Source

The study is funded by the National Institutes of Health (National Cancer Institute).

4.0 SAFETY CONSIDERATIONS

We believe this protocol/study will be minimal risk. The proposed home visits and biosample and data collection pose minimal risk to participants. Anthropometric measurements are all non-invasive. There would be a blood draw (thus potential for brief mild pain) associated with any home visit (1 to 2 over the

course of the study for any given participant). The study team will ensure that the amount drawn at any visit is safe from a blood volume standpoint. It is possible, but unlikely, that some survey questions may cause participants to feel uncomfortable. All instruments proposed have been previously used in other research. For participants selected to participate in the randomized intervention trial, it is possible that receipt of clinical lab results may cause some participants to feel uncomfortable or anxious. Similarly, receipt of a SCP with an individual's predicted cardiovascular risk may cause anxiety or discomfort. We will be monitoring self-reported anxiety and depression as part of our study. Prior CCSS studies have not shown that receipt of such survivorship care plans to be a source of significant anxiety.⁴³ We feel that providing such information, even when unexpected, may be important and have important future health consequences, as the research data to be provided to participants are all results with clinical interpretation and significance. For participants on the intervention arm, they will get a phone or web video session by which any results are given and explained to them by a survivorship trained clinician, approximating a normal clinical exchange. Participants on the control arm will only get a letter summarizing clinically relevant results, and will be encouraged to discuss any abnormal results with their primary healthcare provider. The study has in place, a process by which critical test results will be reported to the study team in real time, in which case, the PI or his designee, can notify the participant more quickly to seek medical follow-up. This process is similar to and adapted from that used by the CDC-sponsored NHANES for their in-person mobile assessments. For participants (either intervention or delayed control) with clinically actionable results but who have no current healthcare provider, the study team has access to resources to aid participants in finding providers in their area who have expertise in treating survivors of childhood cancer. This will be clearly explained on their results letter.

5.0 SUBJECT ELIGIBILITY

5.1 Inclusion Criteria

For Primary Aim 1:

- 5.1.1 CCSS participant who is age ≥ 18 years at time of initial consent.
- 5.1.2 High CV risk status based on CCSS risk prediction models for cardiomyopathy and ischemic heart disease.
- 5.1.3 Living in the U.S., within 50 miles of a designated exam service provider (e.g., EMSI) based on CCSS's available contact information at the time of approach.
- 5.1.4 Able to read, write, and speak English.
- 5.1.5 Ability to understand and the willingness to provide informed consent.

For Primary Aim 2, in addition to the satisfying the above criteria, participants must also meet the following criteria:

5.1.6 Abnormal CV condition identified on home visit. Defined as having at least one of the following:

- Average blood pressure $\geq 130/80$ mmHg ($\geq 130/80$ if existing hypertension diagnosis)
- LDL ≥ 160 mg/dL
- Triglyceride ≥ 150 mg/dL (if ≥ 10 hours fast) or ≥ 200 mg/dL (if < 10 hours fast)
- If not known to be diabetic: Glucose ≥ 100 mg/dL (if ≥ 8 hours fast) or ≥ 140 mg/dL (if < 8 hours fast)
- HbA1c $\geq 5.7\%$ (if not known to be diabetic), HbA1c $\geq 7\%$ (if known diabetic).

5.1.7 Be free of any known (self-reported) ischemic heart disease or cardiomyopathy.

5.1.8 Have access to a telephone or computer to receive a phone or web video counseling/intervention session at baseline and at 4 months.

5.2 Exclusion Criteria, applicable to all participants

5.2.1 Individuals with known cardiomyopathy or ischemic heart disease based on prior CCSS surveys are excluded. While not likely to be common, participants who *newly* report in our study's baseline survey that they have cardiomyopathy or ischemic heart disease can have a home visit completed but will then be done with the study regardless of their home visit results.

5.2.2 Not currently known to be pregnant; individuals known to be pregnant and otherwise eligible for the study can be enrolled once no longer known to be pregnant. Participants who report being pregnant AFTER randomization can remain in the study.

5.2.3 Individuals receiving active cancer treatment. Participants who report starting active cancer treatment AFTER randomization can remain in the study.

6.0 SUBJECT RECRUITMENT & REGISTRATION

6.1 Recruitment

A list of eligible patients for Aim 1 will be generated using existing CCSS data. Staff at the CCSS Data Coordinating Center at St. Jude will be responsible for sending out approach packets to these patients (introductory letter, Consent, Healthcare Provider Form, HIPAA, study questionnaire, and upfront honorarium). We will also have the Consent/ Healthcare Provider Form/ HIPAA Form and the study questionnaire available online. For non-responders, St. Jude interviewers will follow-up with phone calls using their standard process. *As part of St. Jude's standard CCSS process for other CCSS activities, participants will have the option of indicating consent by signing the paper form, signing an online consent, or by providing verbal consent to a CCSS St. Jude interviewer.* Similarly, questionnaires can also be completed by interview.

With our 12/2017 protocol modification, we will also pilot alternative approach packets to see if smaller packets that request less of participants upfront can improve accrual. Specifically, in addition to the existing approach process, we will pilot a 2nd process by which we exclude the printed study questionnaire from the approach packet (an option to complete this on-line will still be mentioned in the cover letter). Participants who consent in this fashion but who do not complete the on-line questionnaire will then be sent a paper version. A 3rd process will also be piloted which will feature a tiered consent process by which the initial consent will just be to complete the initial home visit without consenting to the subsequent randomized intervention trial. For those participants who consent in this fashion, after they complete the initial home visit and are found to be eligible for the randomized intervention trial, they will then receive the second consent form that describes the trial. If one of these alternative approach processes results in a substantially higher enrollment rate, that process will then be adopted as our standard approach.

Contact information for interested participants will then be forwarded to a designated exam service provider (e.g., EMSI) who may then directly communicate and schedule a home visit with the participant. As part of the home visit, for those participants who did not provide a paper-signed copy of their HIPAA authorization / Medical Record Release form (since we are unsure electronic or verbal signatures will be acceptable for primary care providers' offices), staff will also ask participants for their willingness to sign a HIPAA authorization and Medical Record Release (to enable the study to obtain their primary care provider's medical records).

[figure not shown]
Based on the study's eligibility criteria, we do not believe patients who are approached will be subsequently found to be ineligible. It is possible (although unlikely) that we may identify someone who has died since their last CCSS contact. CCSS staff at St. Jude are trained to deal with this situation and CCSS records will be updated accordingly. Also unlikely but possible, an otherwise eligible participant may have moved and may now live in at an address outside the exam service provider area. Should this occur, the study will send the participant a thank you/acknowledgment letter indicating that they will not be able to participate this time (**Appendix**).

6.2 Registration

Information on consented patients will then also be forwarded to the Fred Hutch study coordinator and entered into a study specific tracking database. A copy of the signed consent form and HIPAA authorization and Medical Record Release will also be sent to the Fred Hutch study coordinator.

7.0 TREATMENT PLAN

7.1 Treatment Plan Overview

7.2 Assignment of Study Group

Among those who meet eligibility criteria for primary aim 1 but not primary aim 2, participation will end after the 1st home visit. Similarly, if we adopt a tiered consent process, those who could be eligible for aim 2 but who do not provide consent to the randomized intervention portion of the study, their participation will end after the 1st home visit.

Among participants who meet eligibility for primary aim 2, there will be a computer randomization on a 1:1 basis to intervention: control assignment, with the control group eligible to receive the intervention on a delayed basis (following the 2nd home visit). The study's goal will be to review in-person collected test results in real-time (within 1-2 days of being received at St. Jude) and determine eligibility with randomization assignment the same day. Given the intervention, it cannot be blinded to

either participant or study clinician. Staff who perform the home visits and the study biostatisticians will be blinded to the study group assignment.

7.3 Intervention Group

The intervention is a personalized clinician-led SCP-focused self-management counseling session that is generalizable to a real clinical setting. A printed SCP with personalized health history, recommendations, and clinically meaningful results from the initial home visit (i.e., average blood pressure, lipid profile, diabetes screening, BMI) will first be mailed to survivors on the intervention arm. We will then schedule participants for a remote counseling session via telephone or HIPAA-compliant web video if the participant prefers. The 1st session with a study clinician will ideally be ≤30 minutes to review the SCP and make mutually agreed upon goals and an action plan (see **Appendix**). We will ask scripted questions designed to address understanding of the SCP, elicit intentions to act on the SCP information, and elicit potential barriers and their solutions related to any planned actions. After the session, the personalized action plan will be mailed to the participant.

Approximately 4-months after the initial counseling session, participants will schedule a 2nd session by telephone, or HIPAA-compliant web video if the participant prefers, with the study clinician to follow-up on the action plan, address any barriers to the plan and mutually agree on a revised plan if needed (ideally ≤15 min). The clinician will also rate the survivor's completion of the action plan from 0 (none of the plan completed and no apparent intention to complete the plan) to 10 (action plan complete; see **Appendix**).

For the both the baseline and 4-month follow-up sessions, the duration of the sessions will be recorded to determine the feasibility of delivering the intervention within the time allotted (≤30 and ≤15 minutes, respectively). The sessions also will be audiotaped for process evaluation of content and fidelity of the clinician adherence to the intervention manual. This is further described in **Section 8**.

7.4 Delayed Intervention Control

Survivors in the control arm will receive a copy of clinically meaningful baseline home visit results, with a general recommendation to seek medical follow-up in instances where any of those values are abnormal since we consider it unethical to withhold such information. A copy also will be sent to their designated healthcare provider. *As such, the control group's health may be improved simply by study participation.* At 4-months, participants will receive a generic thank you letter by mail for participating. This will include a reminder of the 2nd home visit, and to enhance control group retention, control participants will be told that they can receive the study intervention (minus the 4-month booster session) after completing the 2nd home visit and any associated surveys. This will include reviewing an SCP and self-management strategies with the study clinician, but we will avoid using those exact terms to minimize control group contamination.

7.5 Interaction with Primary Healthcare Providers

All participants, at time of consent, will be asked to list their current and past (within the last 2 years) primary healthcare provider(s). Current designated providers will receive a copy of all materials sent to study participants. Thus, healthcare providers of participants randomized to the intervention arm will be mailed a print copy of the SCP with home visit results and the survivors' personalized action plan. We will directly send the SCP to providers because studies have shown that reliance on survivors alone to disseminate a copy of their SCP to their provider is problematic.^{46,55} An analysis of existing CCSS data showed that receipt of a print media intervention and fostering increased survivor-physician dialogue was associated with increasing adherence to screening.²⁶ Providers can contact the research team with

any questions regarding the SCP and action plan contents.

- Following the 1st home visit, healthcare providers designated by participants randomized to the control arm will be mailed a print copy of the home visit results only.
- Following the 2nd home visit, healthcare providers of participants on both study arms will be surveyed with regards to their self-efficacy (including self-reported knowledge) towards providing care for childhood cancer survivors. The survey will be accompanied by a cover letter, copies of clinical results (both groups), a SCP (intervention group only), and the patient's signed HIPAA authorization and Medical Record Release (if available), requesting records from the past 3 years. If the budget permits, the study will provide an upfront honorarium to providers (not exceeding \$20). Non-responding providers will receive a 2nd survey packet (inclusive of clinical results, SCP if applicable, and the signed HIPAA authorization and Medical Record Release if available) approximately a month later with an alternative cover letter. No honorarium will accompany the 2nd packet. This will be faxed to the provider's office if a fax number is available, and/or mailed. We will repeat this process two more times if no response is received after another month.

For participants (either intervention or delayed control arm) with clinically actionable results but who have no current healthcare provider, the study team has access to resources to aid participants in finding providers in their area who have expertise in treating survivors of childhood cancer. This will be clearly explained on their results letter and by phone or web-video.

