8.8 Primary healthcare provider measurements

Following the 2nd home visit, accompanying the mailing of a copy of participant materials (intervention group: clinical results and SCP; control group: clinical results only), all designated providers will be asked to answer questions adapted from the NCI/ACS SPARCCS (see **Appendix**).⁶¹

We will also request outpatient clinical records (clinician notes, medication lists, laboratory results) spanning the study period (and up to 2 years prior to the 1st home visit) from all participants' primary healthcare providers. We will abstract records for: 1) documentation of the participant's prior cancer history and CV risk status in relation to past cancer exposures; 2) any reference to a SCP or long-term follow-up guideline; 3) any CV screening planned or undertaken [coded separately]; 4) presence of any of the three target CV risk factors as a diagnosis/problem; and 5) interventions to address any CV risk factor [coding lifestyle or drug prescription separately]. Medications will be reviewed to examine whether, among those undertreated at the 1st home visit, there is subsequent treatment intensification (e.g., going from lifestyle prescription alone to adding medication; from lower to higher drug doses; from single to multiple drugs; **Table 7**), and whether treatment intensity differs across study arms after the intervention.

Medication (class)	Low	Medium	High
Hypertension			
Lisinopril (ACE-inhibitor)	≤10	11-30	>30
Amlodipine (calcium channel blocker)	≤2.5	2.6-9.9	≥10
High cholesterol			
Simvastatin (HMG CoA reductase inhibitor)	<20	20-39	≥40
Diabetes			
Glipizide (sulfonylurea)	<10	10-19	≥20
Insulin			Any dose

Description of how the study will engage with primary healthcare providers is otherwise described in **Section 7.5**.

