8.9 Materials returned to participants and primary healthcare providers

Information the study will send (by mail) back to study participants and their designated current primary healthcare provider are summarized in **Table 8**.

TABLE 8. Information the study will mail back to study participants and their current primary healthcare providers.

After the initial home visit / baseline counseling session	After the 4-month booster	After the 2 nd home visit

Intervention group (participant & provider)	Clinical results Survivorship care plan Action Plan	Updated Action Plan	Clinical results Survivorship care plan
Control group (participant & provider)	Clinical results	-	Clinical results Survivorship care plan*

*Mailing of the care plan would not occur until AFTER the control group's designated healthcare providers are surveyed.

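### The 1-year provider survey and its reminders enclose a fresh care plan in the intervention arm only, so the provider self-ratings cannot separate the plans sent during the year from the copy in hand while answering.

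*Combined protocol and SAP*

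**What the plan says.** Section 7.5 describes the packet sent to providers after the 2nd home visit: "The survey will be accompanied by a cover letter, copies of clinical results (both groups), a SCP (intervention group only"). Non-responders get a "2nd survey packet (inclusive of clinical results, SCP if applicable, and the signed HIPAA authorization" and records release, and then: "We will repeat this process two more times if no response is received after another month". That makes up to four packets, each with an SCP in the intervention arm and none with one in the control arm. Section 8.8 confirms the difference, with the survey "accompanying the mailing of a copy of participant materials (intervention group: clinical results and SCP; control group: clinical results only"). The footnote to Table 8 (section 8.9) holds back the control arm's plan: "Mailing of the care plan would not occur until AFTER the control" arm's providers have been surveyed.

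The second SCP is a planned element of the intervention arm. Section 2.3 states: "Providers of intervention study participants also will receive a copy of the SCP with personalized recommendations following both home visits". Intervention providers have by then already been sent the baseline SCP, the action plan and the updated action plan (section 7.5 and Table 8).

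The provider outcome is self-rated self-efficacy, including self-reported knowledge (7.5). It is measured at 1 year only (3.1.3) and compared between arms by chi-square tests (13.3). Hypothesis 2 of Aim 3 expects that "healthcare providers who received the SCP will report improved knowledge and self-efficacy towards CV risk and survivorship care vs. providers of controls".

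**The concern.** The control arm answers with clinical results on the desk. The intervention arm answers with clinical results and a fresh document on the very subject of the questions. If having that document in hand raises self-ratings, the arm difference contains two things: whatever the mailings during the year achieved, and whatever the enclosure did on the day. There is no provider baseline and no intervention packet without an SCP, so no planned analysis can divide them.

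This matters because section 3.3.3 defines the Aim 3 endpoint as barriers that contribute to undertreatment. The enclosed copy is mailed after the 2nd home visit and cannot have influenced the blood pressure, lipid or glucose values found there. A positive provider result could therefore partly reflect something that could not have acted on the 1-year outcome. Section 13.3 anticipates that the SCP may change who responds, but not that it may change how they answer.

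**Working it through.** **Packet contents.** The documents contest no figure here, so the first step is to set the mailings side by side.

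| Mailing | Intervention provider | Control provider |
|---|---|---|
| After 1st home visit | results, SCP, action plan | results |
| After 4-month booster | updated action plan | none |
| 1-year survey packet | results, survey, **SCP** | results, survey |
| Up to 3 reminders | results, survey, **SCP** | results, survey |
| After the survey | no further mailing listed | SCP |

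The rows before the survey are the treatment during the year. The bold entries coincide with the measurement. Every intervention responder has both exposures and every control responder has neither, so the data contain no contrast between them.

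**How large could it be?** The documents give no size for the effect of an enclosed copy. The illustration below uses these inputs:

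- Favourable answers in controls: 10% (Table 10, provider self-efficacy row).
- Survivors with complete data: 190 per arm (section 13.2, after 20% drop-out).
- Provider response: 19%, the participation in an earlier SCP study (section 2.2), as a low case; 50%, assumed; 100%, as the ceiling for 190.
- Responders per arm: 0.19 × 190 = 36.1, so 36; 0.50 × 190 = 95; 1.00 × 190 = 190. The 87% retention of the earlier randomized trial (section 2.2) would instead give 0.87 × 240 = 208.8, so 209.
- Plans sent during the year: assumed to have no effect. The enclosed copy alone is assumed to lift favourable answers to 12.5%, 15% or 20%.

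The test is the Pearson chi-square without continuity correction, two-sided 5%. With n per arm, x₁ and x₂ favourable answers and pooled p = (x₁ + x₂)/(2n), it rejects when (x₁/n − x₂/n)² / [p(1 − p)(2/n)] > 3.841. The rejection probability is the sum, over all rejecting pairs, of the product of the two binomial probabilities.

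| Responders per arm | No lift | 12.5% | 15% | 20% |
|---|---|---|---|---|
| 36 | 0.058 | 0.070 | 0.105 | 0.225 |
| 95 | 0.051 | 0.085 | 0.180 | 0.494 |
| 190 | 0.050 | 0.120 | 0.314 | 0.788 |
| 209 | 0.049 | 0.126 | 0.339 | 0.825 |

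These are chances of a significant arm difference attributable to the enclosed copy. With few responders or a small lift, they are close to the no-lift column.

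**The secondary logistic model.** Section 13.3 also relates provider ratings to persisting undertreatment, adjusting for randomization status. This was checked with 3,000 simulated trials of 190 per arm, favourable ratings 10% (control) against 20% (intervention), and ratings independent of undertreatment within each arm. Using a likelihood-ratio test for the rating:

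- Undertreated 90% against 79% (the planning RR of 0.88): significant in 5.4% with arm in the model, 7.2% without.
- Undertreated 50% against 35.5% (RR 0.71): 5.5% with arm, 7.6% without.

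The planned adjustment therefore absorbs a lift that is uniform within an arm. Only a lift that varies within an arm could affect this model.

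**The case against.** The strongest reply is that the design matches its own hypothesis. Hypothesis 2 compares providers who received the SCP with providers of controls, and section 2.3 makes the second SCP part of the assigned strategy. A lift from the enclosed copy is then an effect of that strategy, and separating the two copies is a question the protocol never asks. This stands as far as validity goes. A reader might infer that the provider comparison is biased or invalid, or that the percentages above are false-positive rates. The documents support neither reading: the randomized contrast of the whole strategy is sound, and the percentages would be power to detect one of its components.

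It is also fair that priming is unproven. The questionnaire is in an appendix that was not available, both arms receive clinical results so some cueing is shared, and intervention providers already hold a baseline SCP. Only the increment from a fresh copy is at issue. The synopsis lists this comparison as a secondary endpoint, and the one analysis tying provider ratings to undertreatment is adjusted for arm.

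The reply does not remove the asymmetry itself. Providers who received the baseline SCP have already received an SCP, so Hypothesis 2 can be tested without enclosing another copy with the questionnaire. The plan already withholds the control arm's SCP until after measurement. It does not do the same for the intervention arm, although Aim 3 is framed around barriers that contribute to undertreatment.

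**Conclusion.** The point holds as a limit on interpretation that is cheap to avoid. Provider self-ratings are collected under different conditions in the two arms, and a positive result could not be read as knowledge or confidence retained from the intervention year. The size is unknown and depends on survey wording not available here. Under the assumed lift from 10% to 15-20%, with no effect of the earlier plans, the enclosed copy alone would give a significant result in about 10-23% of trials with 36 responders per arm, 18-49% with 95 and 31-79% with 190. With a lift to 12.5% the figures are 7%, 9% and 12%.

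A reader might also infer that the main trial result is affected. It is not. The Aim 2 endpoint, the survivor-reported outcomes and the record-abstracted practice changes do not depend on what is enclosed with the provider survey. The change is worth making, but nothing in the primary comparison turns on it.

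**What to change.** Send providers in both arms the same survey packet and the same reminders: cover letter, clinical results as a stand-alone document, survey and records request. Mail the intervention provider's second SCP once the survey is returned or the last reminder has lapsed. This extends the hold that Table 8 already applies to the control arm.

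Three places need editing: section 7.5, both the packet contents and the general rule ("Current designated providers will receive a copy of all materials sent to study participants"); section 8.8; and the Table 8 footnote, so that it covers the provider's copy in both arms. Section 7.6 can stand, since survivors' own copies go out as now. Because that section embeds second-visit results in the SCP, the provider's results must be issued separately.

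If packets have already gone out, record which version each responder received and report the result as self-ratings given with an SCP enclosed. Any comparison between packet versions would be descriptive, because version is not randomized.

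The cost is a delay. Responding intervention providers get the updated SCP when they return the survey. Non-responders get it about three to four months later, since four packets go out roughly a month apart. If response is near the 19% seen earlier, that is about 81% of intervention providers. Baseline SCPs, action plans and second-visit results are not delayed. The fix is partial: providers can still consult the baseline SCP, and a survivor may pass on the new one.
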